We propose a causal model informed by the Wagner Chronic Care Model in which productive disease management interactions between informed patients and prepared care teams are promoted by effective health systems as well as communities.³⁷ Critical relevant elements of the health system are processes to provide self-management support, design of the healthcare delivery system, and technologies such as clinical information systems and decision-support. In our causal model, for patients with chronic disease, access to care is a mediator in the causal pathway between the disruption in care from the pandemic and the outcomes in our study (e.g., unnecessary utilization such as unplanned ED visits, and satisfaction with care). To the extent that telemedicine improves access to care, it mediates this relationship. Furthermore, patient-provider communication is an additional mediator of this relationship, through its effect on self-management support as well as trust in the healthcare system.

However, one reason this study is important is that the abrupt nationwide transition makes it challenging to determine in advance whether telemedicine would be expected to have positive or negative impacts on care access and patient-provider communication, overall and within important patient subgroups. The pandemic prompted telemedicine use by patients who would otherwise not have been early adopters of telemedicine, increasing the diversity of patient users, including those from disadvantaged social circumstances or with older age who may encounter more barriers to successful use of telemedicine (stemming from limited device access, technology literacy, or broadband access, or primary language). These barriers would cause telemedicine to have a negative effect on care access and patient-provider communication, as well as patient satisfaction. Conversely, however, there are known instances in which people who would not have opted into the technology themselves nevertheless become effective users of the technology after being provided with an initial access experience.²⁶ Thus, the forced use of telemedicine may possibly have successfully promoted engagement with telemedicine and therefore improved access to care and patient-providers communication among some patients from less advantaged patient groups.

Another complexity making it challenging to predict the directionality of the effect of the telemedicine transition is that the rapid nationwide transition appears to have led to diverse types of telemedicine programs, ranging from relatively mature programs with well-established technology and user support, to rapidly implemented programs with less well-established technology or support. This heterogeneity may influence whether telemedicine was effective in improving access to care or patient-provider communication. It is well-established that innovations that are not highly usable, well-matched to user needs, and supported with organizational support are unlikely to promote their desired outcomes.^{38,39}

In light of the complexities described above in the causal model, we propose a nondirectional overall hypothesis that telemedicine-only, telemedicine-supplemented in-person visits, and in-person only groups will have different healthcare utilization and patient satisfaction outcomes.

Primary Analysis

Our causal model will leverage variation over time and across sites in the availability of telemedicine visits to assess the impact of a change in clinic-level availability in telemedicine on patient-level outcomes. We will use a generalized version of the difference-in-differences methodology (also known as an event study design) in an intent-to-treat framework to compare patients receiving care at clinics that have switched to telemedicine-only visits at a given time with patients at comparable clinics that have not or that used a mixture of telemedicine and in person care. This event

PRINCIPAL INVESTIGATOR: [name]; [name]

study design allows for multiple treatment periods and for the relationship between treatment and outcomes to vary over time.

The causal identifying assumption in difference-in-differences models is that outcomes in each comparator arm would have followed the same trends in the absence of exposure to telemedicine, after the onset of the pandemic.⁴⁰ While we cannot directly test this assumption, we can test whether there significantly different trends in outcomes during the months prior to the onset of the pandemic. We expect that this parallel trends assumption may hold in our study, because the transition to telemedicine during the pandemic was rapidly implemented and potentially unrelated to patient outcomes and the underlying quality of the clinic.

In order to further improve the comparability of clinics across each of the treatment arms, we will use propensity scores to match clinics based on clinic-level characteristics, including rurality; size; mean clinical risk (HCC score, Elixhauser comorbidity index); and proportions of patients with Medicaid coverage, dually eligible for Medicaid and Medicare, 65 and older, male, and black or Hispanic. In an additional sensitivity analysis, we will exclude patients who tested COVID-positive. We will match clinics based on their baseline characteristics in the pre-pandemic period and their initial treatment arm status after the onset of the pandemic. In addition, we will explore the sensitivity of our estimates to re-matching each month, since, as noted in the intervention section above, treatment status will be time-varying. As part of our descriptive analysis, we will evaluate how often clinics switch treatment arms from their initial treatment status, which will inform our sensitivity analyses.

We recognize that it is possible that the matching procedure might result in the loss of clinics and sample size. If it does, we would instead apply alternative methods that accomplish the goal of propensity score matching (addressing confounding to improve causal estimation) without loss of sample size. The first alternative is inverse probability weighting, which uses the propensity score to re-weight the outcomes, creating a pseudo-sample in which exposure to the intervention is unrelated to potential confounders.⁴¹ The second alternative is doubly robust estimation, which incorporates (i) a propensity score model and (ii) an outcome regression model in order to gain efficiency (more power) in comparison to an inverse weighting, and to reduce reliance on the ability of correctly positing the propensity score model.⁴² We can substitute these approaches for the originally proposed propensity score weighting, or we can instead apply them in a sensitivity analysis.

We will define the degree of telemedicine exposure (dose) in two ways. First, based on the comprehensive landscape survey of primary care leaders in [Aim 1](#), we will develop a composite score indicating the robustness of the telemedicine program at each clinic site under study. Among other features, this score will take into account the total number of components and delivery modes of the telemedicine program, its focus on providing coordinated care to a patient population with chronic care needs, and staff and clinical support from the organization.

Second, we will define telemedicine exposure based on the proportion of all visits at a given clinic that are delivered via telemedicine in each month. Specifically, we will classify clinics into quartiles of telemedicine exposure based on the distribution of all telemedicine provision among clinics in this treatment arm. We will then separately analyze the relationship between our outcomes of interest and the amount (dose) of telemedicine being offered at a clinic. We will cluster all primary and secondary analysis at the clinic level, as this is the level at which the exposure occurred.⁴³

Finally, in addition to the primary intent-to-treat analysis, we are proposing an additional secondary analysis. This secondary “as treated” analysis is designed to evaluate the relationship between patient-level telemedicine exposure and our outcomes of interest. In this secondary analysis, we will characterize patients’ exposure to telemedicine after the first wave of shelter-in-place measures were put into place based on the treatment that they actually received

PRINCIPAL INVESTIGATOR: [name]; [name]

rather than based on the availability of telemedicine at the primary care clinic to which they were attributed. In this analysis, we will adjust for observed clinic and patient-level characteristics as described in the response above that may impact both the availability and choice to use telemedicine, as well as patient outcomes. Additionally, we will provide estimates from a fixed effects model in which each patient serves as their own control.

Primary findings will be presented alongside descriptive statistics assessing the external and internal validity of the analysis, including balance across relevant covariates before and after matching. We will also use descriptive statistics to characterize the analysis population, identify sources of missingness in the data across outcomes and covariates as well as whether missingness may introduce selection bias into our analysis. In sensitivity analyses, we will multiply impute covariates for which there is meaningful evidence of missingness.

Heterogenous Treatment Effects

We hypothesize that patients in disadvantaged sociodemographic groups will derive less benefit from telemedicine than patients in majority groups because of barriers to use of telemedicine described in the conceptual model. We additionally hypothesize that more robust telemedicine programs (as defined in the Aim 1 taxonomy) will provide more benefit to patients than less robust ones.

We will explore variation in effects for the outcomes listed in Table 1 among pre-specified sociodemographic subgroups (race/ethnicity, rurality, median income for zip code) and clinical subgroups (COVID-19 patients vs. all other patients; low vs. high burden of illness; stable vs. unstable disease, as indicated by clinical measures of disease progression). Finally, we will use the Aim 1 survey for stratified analyses of telemedicine factors, such as historical use of telemedicine and patient technical assistance. Additionally, the Medicare data will allow us to conduct a subgroup analysis for our claims-based outcomes on dually eligible patients. Therefore, we will conduct eight separate subgroup analyses in all. We will use the same analytic approach described in the primary analysis to conduct these subgroup analyses and present the differences in treatment effect estimates with standard errors. We will also conduct univariate subgroup analyses with interaction effects to statistically test for differences in outcomes (as outlined below) among these subgroups.

The goal of these subgroup analyses is to evaluate the effects of each of the three telemedicine arms across patient populations which may have unequal access to telemedicine visits, experience differential treatment effects of telemedicine use, and vary in experiences with regards to using telemedicine. In particular, individuals with lower digital health literacy and higher illness burden may be affected differentially by the adoption of telemedicine-supplemented or telemedicine-only care relative to in-person care only. Previous work has also shown that older adults (aged 65 and older) have lower digital health literacy, and individuals in rural areas are more likely to face greater barriers accessing telemedicine.^{44,45} Previous work has also reported that black patients were less likely to use an inpatient portal relative to white patients, although recent work has shown that during the COVID-19 pandemic, blacks may be more likely than whites to report using telemedicine.^{46,47} We hypothesize that the comparative effectiveness of the treatment arms will differ significantly across the following subgroups: race/ethnicity, rurality, income as proxied by payer and median income for zip code.

G. ETHICS AND DISSEMINATION – AIMS 1 AND 2

Research Ethics Approval

PRINCIPAL INVESTIGATOR: [name]; [name]

BRANY, an independent fully AAHRPP-accredited IRB, will serve as the IRB of record for this study. An exempt approval was received by BRANY on 11/16/2020. Local IRBs will be obtained at the participating sites by the expected deliverable date (2/15/21).

All protocol modifications will be disseminated to relevant parties, including all participating investigators and sites, the IRB, and PCORI.

Confidentiality

Investigators will maintain strictest standards for confidentiality and privacy of all research data. For Aim 1 interviews, data will be recorded, stored, and analyzed using study-specific IDs rather than participant name; the list linking name to ID will be stored securely and accessible only to the site PIs. Transcription will be done by a HIPAA compliant vendor. Any mention of identifying information will be stripped from the interview transcript before it is saved and analyzed. Direct access to the data will be limited to authorized research personnel named on the IRB. For Aim 2 analyses, quantitative analyses will be performed on limited data sets containing no individually identifying information other than dates. Data security will be maintained as described above in the data management plan. No efforts will ever be made to re-identify any research data.

Declaration of Interests

All investigators have completed a Conflict of Interest Disclosure Form. None of the Principal Investigators ([name], [name], [name], [name], [name], [name]) have any financial or competing interests.

Access to Data

As described under the Data Management Plan, primary data analysis will occur within Weill Cornell's Data Core, a secure research computing environment that meets all relevant standards for working with potentially identifiable patient information. The Weill Cornell coinvestigators named on the Medicare DUA will have access to the data set for the primary analysis. In light of the need for speed in this 2 year project, secondary analyses involving commercial claims data will be conducted by the payer coinvestigators, who will have full access to these secondary data sets. Raw data sources and analytic files will be maintained within the secure computing environments for two years following conclusion of the project.

Dissemination Policy

These studies have great potential for dissemination and implementation in light of national interest in telemedicine, driven by patient questions about the benefits of telemedicine, primary care practice concerns on how to effectively and safely provide services after COVID-19 shelter-in-place orders expire, and the desire by public and private payers for actionable guidance on whether to extend coverage and reimbursement for telemedicine. The findings from our research will include: a taxonomy and explanation of pragmatic telemedicine initiatives as deployed in the field (which will have value to policymakers and researchers seeking clarity about terms and definitions in use); a nuanced understanding of provider and patient perspectives, including both advantages and barriers to use (of interest to patient and provider stakeholders); and rigorous evidence about the comparative effectiveness of telemedicine relative to traditional models of in-person care (of value to policymakers, payers, providers, and patients).

Results from these studies will be disseminated in multiple ways. We anticipate publishing results to top medical and scientific journals. The research team has an impressive publication record of hundreds of peer-reviewed scientific

PRINCIPAL INVESTIGATOR: [name]; [name]

articles, including many in high-profile journals. In addition, all are active members of national and international scientific organizations and routinely present interim and final findings at the PCORI Annual Meeting, AcademyHealth, the American Medical Informatics Association, the American Public Health Association, and many other venues. Findings will be disseminated in more approachable, non-technical language through social media and study-specific websites. Finally, we will work with our Stakeholder Board to assess stakeholder interest in an actionable toolkit of recommendations for telemedicine implementation.

All reports and publications will be designed to provide sufficient information to allow for assessment of the studies internal and external validity.

Authorship eligibility guidelines will be determined using the International Committee of Medical Journal Editors' (ICMJE) definition of authorship, which is based on the following 4 criteria:

- 1) Substantial contributions to the conception or design of the work; or the acquisition, analysis, or interpretation of data for the work; AND
- 2) Drafting the work or revising it critically for important intellectual content; AND
- 3) Final approval of the version to be published; AND
- 4) Agreement to be accountable for all aspects of the work in ensuring that questions related to the accuracy or integrity of any part of the work are appropriately investigated and resolved.

One goal of our work with patient and stakeholder partners will be to define barriers to telemedicine implementation. The pragmatic design of our research and the broad inclusion criteria will make our findings more generalizable. We anticipate that our findings will result in actionable guidance. Some health care organizations, however, may face significant financial constraints, which limit their ability to act on all study findings and recommendations. To address this concern, our research design is intended highlight which patient groups are most likely to benefit from specific telemedicine interventions, which could help providers target telemedicine initiatives efficiently. We will identify other potential barriers to implementation and address them through Aim 1 and our engagement plan.

H. ENGAGEMENT APPROACH

Stakeholder input will be elicited to identify telemedicine leaders, patients, and providers to participate in Aim 1, propose new comparator groups for Aim 2, suggest additional outcomes for analysis in Aim 2, disseminate study results to stakeholder groups, and discuss applications of findings to inform practice and policy. **Stakeholders we will engage** include: (a) patients with the five chronic diseases of interest; (b) primary care providers, (c) primary care practice leaders and technology leadership who build, support and resource telemedicine; (d) allied health professionals (i.e., social work, nursing) who support implementation; and (e) payers who seek to decide what telemedicine components they will cover. We have already begun to recruit stakeholders and the engagement leads for the three collaborating CRNs, led by [name] for INSIGHT, will identify other stakeholders. **The engagement approach** will follow the accelerator model, a stakeholder-engaged research model in which stakeholders from different disciplines come together to share expertise, experience, and resources as equals.⁴⁸ Coinvestigators [name] (Mount Sinai site PI), [name] (INSIGHT engagement lead), and [name] (multiple PI) have years of experience with this approach.⁴⁹ Other accelerators in operation are supporting the PCORI-funded natural experiment in diabetes research,⁵⁰ and other big data analyses similar to the proposed project.⁵⁰ In the accelerator, a national **Stakeholder Board** will inform all aspects of the study through regular meetings. **Workgroups** reporting to the board will include additional members from research sites and focus on specific study aspects, including outcome selection, results interpretation,

PRINCIPAL INVESTIGATOR: [name]; [name]

and dissemination. For **co-learning**, we will build capacity of all team members through team science work and educational activities.⁵¹⁻⁵³ Board members will be invited to co-author and co-present research findings to scientific and lay audiences. We will foster **trust, transparency, and honesty** through clear delineation of roles and responsibilities, regular communication, and anonymous feedback about meeting effectiveness and operations.

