Additionally, we will collect patient-reported outcomes (PROs) through REDCap surveys of 1,000 patients at Weill Cornell Medicine, delivered via the patient portal. The recruitment methods for this survey include, but are not limited to, the use of the Consent to be Contacted for Research (CCR) (WCM IRB protocol 1812019822; PI: [name]). For those patients who have opted into CCR participation and meet the inclusion criteria for this study, the study team will send recruitment message(s) via approved methods in accordance with CUIMC-NYP-WCM governance. By requesting CCR status for patients meeting study eligibility criteria, the study team agrees to contact only patients approved by the Institutional Review Board (IRB) for this specific study. The study team agrees to adhere to EpicTogether and the Tripartite processes. Contingent on the Tripartite committee(s)'s decision, all the relevant materials will be submitted in subsequent submissions to the IRB. The recruitment methods for patients who are approved to be contacted include, but not limited to, use of Epic's research recruitment message, phone call, email, and/or mail. The study team also agrees to maintain a record of patients contacted for, enrolled in, declined for, and withdrawn from the study, which the team will share at regular intervals with TRAC and the IRB. For patients who have not consented to be contacted for research, the study team will pursue the alternative methods of recruitment approved by the IRB office. Additional recruitment methods for the PRO survey include inviting patients who were recruited for the qualitative interviews, or patients who are nominated by their primary care providers. Invitations will be sent to patients via email, phone call and/or mail.

We will collect PROs on patient experiences based on the Patient Satisfaction Questionnaire (PSQ-18) (5-point subscale),²⁹ which includes patient satisfaction, communication quality with providers, and accessibility/convenience of care. For individuals who accessed a telemedicine visit, we will ask questions adapted from the validated Telemedicine Usability Questionnaire (TUQ), including the ease of use and access to the telemedicine service, quality of the interaction with the provider, and satisfaction.⁵ We will leverage stakeholder input and the Aim 1A survey to inform the duration of patient exposure to each of the three treatment arms.

Table 1

Measure	Data Source
PRIMARY OUTCOMES	

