For the patient satisfaction outcome, with our planned survey sample size of patients with patient-reported outcomes ($n = 1,000$), we have 93% power to detect a 5% difference in patient satisfaction between the treatment and comparison arms in a two-tailed test with an alpha of 0.05. Based on an RCT examining the impact of an intensive outpatient care program on patient-reported satisfaction among a cohort of high-need patients, we need sample size of 206 patients to provide 80% power to detect a 0.26 difference in patient satisfaction (effect size determined by the study) using a 2-tailed hypothesis at an α level of .05.³⁴ Our sample size of 1,000 patients will provide greater than 80% power to detect this difference. The 0.26 difference in patient satisfaction was derived from a recent research study evaluating the impact of a medical home program on patient-reported satisfaction.⁸ The measure of patient satisfaction was based on a

PRINCIPAL INVESTIGATOR: [name]; [name]

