Our sample sizes still provide sufficient power should we adopt a non-inferiority framework to test whether telemedicine visits are no less effective than in-person visits. For the ED visit outcome, if we assume that the minimum sample size is 25,000 in each of the three groups, and that between 20% and 5% of patients in the in-person arm have unplanned ED visits, we will have between 80% and 99% power to determine whether the telemedicine arm is no worse than 1 percentage point (absolute) lower than the in-person comparator. (This calculation was done with a z-test to determine a difference in proportions with a one-sided 2.5% significance level.) In fact, our study will have more power if the groups have more than 25,000 patients. For the patient satisfaction outcome, with 500 in each group, there will be 90% power with one-sided level of significance of 0.025 to determine if the decrease in mean level of patient satisfaction for the telemedicine group is no more than 0.2 standard deviations compared to the control group (in-person). We believe a 0.2 standard deviation effect size is reasonable for a non-inferiority margin because it lies below the 0.25 effect size that is typically deemed meaningful for patient satisfaction and quality of life instruments.

F. AIM 2 METHODS: DATA COLLECTION, MANAGEMENT, ANALYSIS

Data Collection Methods and Data Sources

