**After submission of this grant, the three participating CRNs agreed to begin collecting data that would allow us to distinguish between telemedicine and in person visits, an item that was not available when this study was designed. This may enable us to conduct a separate analysis of telemedicine versus non-telemedicine visits at the visit level.*

Finally, we will collect PROs using REDCap surveys through the WCM REDCap database. REDCap is a secure website for building and managing online surveys and databases. It is available at each site and harmonized across institutions to facilitate data storage and management. REDCap will generate automated emails or text messages to patients containing hyperlinks to access surveys. The REDCap team will be responsible for maintenance during the study period. Table 4 summarizes the primary data sources and data elements.

Table 4

Data Sources	Data Elements
Medicare, Commercial claims, CRN structured EHR data	Diagnosis codes
Medicare, Commercial claims, CRN structured EHR data	Procedure codes
Medicare, Commercial claims, CRN structured EHR data	Demographic characteristics
Medicare, Commercial claims, CRN structured EHR data	Health care utilization
Commercial claims, CRN structured EHR data	Laboratory testing results
Medicare, Commercial claims, CRN structured EHR data	Medications
REDCap surveys	Patient experience and satisfaction

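### The 90% power for satisfaction non-inferiority assumes 500 v 500, the whole 1,000-patient survey, although the satisfaction hypothesis has three arms and the telemedicine test group is not identified

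*Combined protocol and SAP*

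**What the plan says.** The last paragraph of the Power Calculation (section E, Aim 2) says that the sample sizes remain adequate if a non-inferiority framework is adopted. For satisfaction it states that "with 500 in each group, there will be 90% power with one-sided level of significance of 0.025". The test is whether the decrease in mean "patient satisfaction for the telemedicine group is no more than 0.2 standard deviations compared to the control group (in-person").

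The survey total is fixed elsewhere. The Outcomes section plans "REDCap surveys of 1,000 patients at Weill Cornell Medicine", and the superiority statement in the Power Calculation uses the same total ("with our planned survey sample size of patients with patient-reported outcomes", n = 1,000).

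The number of arms is three. Under Causal Model and Overall Hypothesis (section F), the nondirectional hypothesis is that the telemedicine-only, telemedicine-supplemented and "in-person only groups will have different healthcare utilization and patient satisfaction outcomes". In the same non-inferiority paragraph, the emergency department calculation assumes that "the minimum sample size is 25,000 in each of the three groups". Table 1 lists patient-reported outcomes among the primary outcomes.

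No section gives expected survey numbers by arm, sets a quota by arm, or says which telemedicine arm or arms make up the telemedicine group in the satisfaction test.

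**The concern.** Two groups of 500 leave no surveys over. If the telemedicine group means telemedicine-only, nobody remains for the supplemented arm. If it means both telemedicine arms pooled, 500 v 500 holds only when exactly half of the respondents belong to in-person clinics, and the plan does not say that it expects this. The emergency department sentence just before it is sized on three groups, and the plan does not explain the change to two.

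At stake is the claim of adequate power. If the contrast finally tested leaves out an arm or is unbalanced, the chance of showing non-inferiority when satisfaction is truly equal is lower than stated. A reader of the plan cannot tell by how much.

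**Working it through.** **Inputs from the plan.** Margin 0.2 SD, one-sided alpha 0.025, 500 per group and stated power 90% (Power Calculation); 1,000 surveys in total (Outcomes and Power Calculation); three arms compared on satisfaction (Causal Model and Overall Hypothesis).

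**Inputs assumed.** True difference zero, because the plan states none; equal SD in the groups; 1,000 completed surveys; no clustering, because the plan gives no intraclass correlation.

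**Formula.** On the standardised scale, power = Φ(0.2 / √(1/n1 + 1/n2) − 1.960).

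**Step 1: is zero difference the plan's own convention?** The emergency department figures in the same paragraph can be checked with Φ(0.01 / √(2p(1 − p)/25,000) − 1.960).
- p = 0.20: 0.01/0.003578 = 2.795, less 1.960 = 0.835, power 79.8% (stated 80%).
- p = 0.05: 0.01/0.001949 = 5.130, less 1.960 = 3.170, power 99.9% (stated 99%).

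Zero difference fits those figures.

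**Step 2: reproduce the satisfaction figure.** 500 v 500: √(2/500) = 0.06325; 0.2/0.06325 = 3.162; less 1.960 = 1.202; power 88.5%. This agrees with the stated 90% to rounding. Exactly 90% would need 526 per group.

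**Step 3: upper bound.** For n1 + n2 of at most 1,000, the sum 1/n1 + 1/n2 is smallest at 500 and 500. So 88.5% is the maximum for any split of the survey under these assumptions.

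**Step 4: other splits.** These are illustrations; the plan states no allocation.

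| Contrast | n1 v n2 | Surveys outside the contrast | Power |
|---|---|---|---|
| Two equal groups | 500 v 500 | 0 | 88.5% |
| Small third arm | 450 v 450 | 100 | 85.1% |
| Pooled telemedicine v in-person, equal thirds | 667 v 333 | 0 | 84.6% |
| Larger third arm | 400 v 400 | 200 | 80.7% |
| Telemedicine-only v in-person, equal thirds | 333 v 333 | 334 | 73.3% |

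For the last row: √(2/333) = 0.07750; 0.2/0.07750 = 2.581; less 1.960 = 0.621; power 73.3%, a miss rate of 26.7%. By the same formula the miss rate at 500 v 500 is 11.5%.

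**Step 5: where 80% is lost.** 393 v 393 gives 80.06% and 392 v 392 gives 79.96%. With two equal compared arms, power is at least 80% while the third arm holds no more than 1,000 − 2 × 393 = 214 surveys.

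**Step 6: sensitivity to the zero-difference assumption.** The true telemedicine advantage that restores 90% is (1.960 + 1.282) × √(1/n1 + 1/n2) − 0.2. This is 0.005 SD at 500 v 500, 0.018 SD at 667 v 333 and 0.051 SD at 333 v 333.

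**The case against.** The strongest reply is that the paragraph describes a two-group question: telemedicine visits against in-person visits, with in-person named as control. The superiority statement also speaks of a treatment and a comparison arm, and the Outcomes section gives the usability items only to respondents who had a telemedicine visit. Two groups of 500 add up to the planned survey, and the figure recomputes. This much stands. There is no arithmetic error, and the contrast is partly named. If an equal two-group split is intended, about 89% is correct before clustering. But the plan does not say that this is the test. The note on a possible "separate analysis of telemedicine versus non-telemedicine visits at the visit level" concerns data from the clinical research networks and says only that it may become possible. The Data Management Plan does store patient-reported outcomes by encounter, but that does not define a contrast.

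Three stronger readings are tempting, and the documents do not support them.
- A reader might infer that the survey is allocated to three arms, and so is 500 short of the 1,500 that three groups of 500 would need. The Outcomes sentence that mentions three arms says that stakeholder input and the Aim 1A survey will "inform the duration of patient exposure to each of the three treatment arms". That concerns length of exposure, not allocation of surveys. The support for three arms on satisfaction is the overall hypothesis.
- A reader might infer that the study's real power is 73%. That figure needs an equal three-way split and a pairwise test, and the plan states neither.
- A reader might infer that a committed test is underpowered. The framework is conditional, and the plan's primary analysis is of Medicare claims. Several of the splits above also stay at 80% or more.

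**Conclusion.** The point holds as a minor inconsistency between a power statement and the design. The stated 90% applies to an equal two-group split of all 1,000 surveys. The plan's satisfaction hypothesis covers three arms, and the plan identifies neither the telemedicine arm or arms tested nor the arm sizes.

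With a true difference of zero, equal SDs and 1,000 completed surveys, 88.5% is a ceiling. Under assumed equal thirds, power is about 85% with the telemedicine arms pooled and about 73% for telemedicine-only v in-person. All figures are before the clinic-level clustering specified under Primary Analysis. Its effect was not computed, because the plan gives no intraclass correlation.

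Patient-reported outcomes are listed as primary, so the statement is worth correcting. The conditional status of the non-inferiority test limits the consequence.

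**What to change.** In the non-inferiority paragraph of the Power Calculation, state which telemedicine arm or arms form the test group, the arm sizes assumed within 1,000 surveys and the assumed true difference. Replace 90% with the matching power.

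If equal arms are assumed, suitable wording would be: *With 1,000 surveys, 333 per arm and a true difference of zero, power for the 0.2 SD margin is about 73% for telemedicine-only v in-person-only, or about 85% for both telemedicine arms pooled v in-person-only (667 v 333), before clinic-level clustering.*

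If an equal two-group test is intended, say so, define the groups, and give about 89% before clustering.

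The cost is a less favourable stated figure. Survey size, margin and analysis are unchanged.
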